10.1.2. Protocol Defined Safety and PK Assessments

Procedure ¹	Predose	Treatment Period Time point (hours)													
		0	0.5	1	1.5	2	2.5	3	4	6	8	12	24 ²	36 ²	48 ²
12-lead electrocardiogram	X				X	X			X		X	X	X	X	X
Vital signs	X				X	X			X		X	X	X	X	X
Study drug administration		X													
Blood collection for pharmacokinetics	X		X	X	X	X	X	X	X	X	X	X	X	X	X
Urine collection for pharmacokinetics (participants with normal hepatic function) ³	X		X	X	X	X	X	X	X	X	X	X	X	X	X
Urine collection for pharmacokinetics (participants with hepatic impairment) ⁴	X				X					X	X	X	X	X	X
Saliva collection	X		X	X	X	X	X	X	X	X	X	X	X	X	X

¹ When coinciding with safety and/or pharmacokinetic assessments, electrocardiograms, vital signs, and pharmacokinetic blood collections should be performed in said order.

² The 24-, 36-, and 48-hour postdose time points correspond to time points on Day 2 and 3, respectively.

³ Urine collection intervals for participants with normal hepatic function (Group D and Group E, if applicable) include 0 (pre-dose), 0 to 2 hours, 2 to 4 hours, 4 to 6 hours, 6 to 8 hours, 8 to 12 hours, 12 to 24 hours, 24 to 36 hours, and 36 to 48 hours.

⁴ Urine collection intervals for participants with hepatic impairment (Group A, Group B, and Group C) include 0 hour (pre-dose), 0 to 6 hours, 6 to 12 hours, 12 to 24 hours, 24 to 36, and 36 to 48 hours.

10.2. Appendix 2: Study Phases and Treatment Emergent Adverse Events

10.2.1. Study Phases

For Groups A, B, C, D, and E, assessments and events will be classified according to time of occurrence relative to the date/time of the study treatment.

Study Phase	Definition
Pre-Treatment	Date/Time < Study Treatment Date/Time
On-Treatment	Study Treatment Date/Time ≤ Date/Time ≤ Study Treatment Date/Time + 2 Days
Post-Treatment	Date/Time > Study Treatment Date/Time + 2 Days

10.2.1.1. Study Phases for Concomitant Medication

Study Phase	Definition
Prior	If medication end date is not missing and is before enrollment date
Concomitant	Any medication that is not a prior

NOTES:

- Please refer to [Appendix 5: Reporting Standards for Missing Data](#) for handling of missing and partial dates for concomitant medication. Use the rules in this table if concomitant medication date is completely missing.

10.2.2. Treatment Emergent Flag for Adverse Events

Flag	Definition
Treatment Emergent	
 If AE onset date/time is on or after treatment date/time & on or before the treatment stop date/time with 2 days lag time. Study Treatment Date/Time ≤ AE Start Date/Time ≤ Study Treatment Date/Time + 2 days.

10.3. Appendix 3: Data Display Standards & Handling Conventions

10.3.1. Reporting Process

Software

 SAS version 9.3 or higher and WinNonlin version software (version 9.3) and WinNonlin version 6.4 or higher will be used.
Analysis Datasets

 Analysis datasets will be created according CDISC standards SDTM IG Version 3.2 & ADaM IG Version 1.0. For creation of ADaM datasets (ADCM/ADCM1/ADAE), the same version of dictionary datasets will be implemented for conversion from SI to SDTM.
Generation of RTF Files

 RTF files will be generated for all reporting efforts described in the RAP.

10.3.2. Reporting Standards

General

 The current GSK Integrated Data Standards Library (IDSL) will be applied for reporting, unless otherwise stated (IDSL Standards Location: https://spope.gsk.com/sites/IDSLLibrary/SitePages/Home.aspx): 
 4.03 to 4.23: General Principles 5.01 to 5.08: Principles Related to Data Listings 6.01 to 6.11: Principles Related to Summary Tables 7.01 to 7.13: Principles Related to Graphics
Formats

 All data will be reported according to the actual treatment the participant received unless otherwise stated. GSK IDSL Statistical Principles (5.03 & 6.06.3) for decimal places (DP's) will be adopted for reporting of data based on the raw data collected, unless otherwise stated. Numeric data will be reported at the precision collected on the eCRF. The reported precision from non eCRF sources will follow the IDSL statistical principles but may be adjusted to a clinically interpretable number of DP's.
Planned and Actual Time

 Reporting for tables, figures and formal statistical analyses: 
 Planned time relative to dosing will be used in figures (with the exception of individual PK concentration-time figures, where actual relative time will be used), summaries, statistical analyses and calculation of any derived parameters, unless otherwise stated. The impact of any major deviation from the planned assessment times and/or scheduled visit days on the analyses and interpretation of the results will be assessed as appropriate. Reporting for Data Listings: 
 Planned and actual time relative to study drug dosing will be shown in listings (Refer to IDSL Statistical Principle 5.05.1). Unscheduled or unplanned readings will be presented within the subject's listings. Visits outside the protocol defined time-windows (i.e. recorded as protocol deviations) will be included in listings but omitted from figures (mean figures only for PK concentrations), summaries and statistical analyses (excluding statistical analyses of PK parameters).

Unscheduled Visits	

 Unscheduled visits will be considered when calculating baseline and in Table 2.9 and Table 2.10, but will not be included in any other summary tables. Unscheduled visits will not be included in figures. All unscheduled visits will be included in listings. 	
Descriptive Summary Statistics	
Continuous Data	Refer to IDSL Statistical Principle 6.06.1
Categorical Data	N, n, frequency, %
Graphical Displays	

 Refer to IDSL Statistical Principals 7.01 to 7.13. 	

10.3.3. Reporting Standards for Pharmacokinetic

Pharmacokinetic Concentration Data	
Descriptive Summary Statistics, Graphical Displays and Listings	
Refer to IDSL PK Display Standards. Refer to IDSL Statistical Principle 6.06.1.
 
For continuous data:
 
 NQs at the beginning of a participant profile (i.e. before the first incidence of a measurable concentration) are deemed to be zero as it is assumed that in this circumstance no drug is yet measurable in the blood. For NQs at the end of the participant profile (i.e. after the last incidence of a measurable concentration); 
 for individual plots and pharmacokinetic analyses these are dropped (set to missing) as they do not provide any useful information (and can erroneously indicate that absolutely no drug is present) for summary statistics, these are set to 0 (to avoid skewing of the summary statistics) Individual NQs which fall between two measurable concentrations are set to missing (individual values of this nature are assumed to be an anomaly) 
If two or more NQ values occur in succession between measurable concentrations, the profile will be deemed to have terminated at the last measurable concentration prior to these NQs. For the purpose of individual participant plots, these NQs will be set to 0, and the subsequent measurable concentrations will be retained. For the derivation of pharmacokinetic parameters, these NQs and any subsequent measurable concentrations will be omitted (set to missing).
 
Note: Concentration values will be imputed as per GUI_51487 for descriptive summary statistics/analysis and summarized graphical displays only.

Pharmacokinetic Parameter Data	
Descriptive Summary Statistics, Graphical Displays and Listings	
N, n, geometric mean, 95% CI of geometric mean, standard deviation (SD) of logged data and between geometric coefficient of variation (CV_b (%)) will be reported.
 $CV_b (\%) = \sqrt{(\exp(SD^2) - 1) * 100}$ 
(SD = SD of Ln-Transformed data)

Parameters Not Being Ln-Transformed	T _{max} , t _{lag} , CL _r , lambda _{z_lower} , lambda _{z_upper} , and lambda _{z_no.} of points.
Parameters Not Being Summarized	lambda _{z_lower} , lambda _{z_upper} , and lambda _{z_no.} of points.
Listings	Include the first point, last point and number of points used in the determination of λ _z and R _{sq_adjusted} for listings.

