10.3. Statistical Analyses

10.3.1. Pharmacokinetic Analyses

Plasma and urine concentrations of gepotidacin will be subjected to PK analyses using noncompartmental methods. Based on the individual concentration time data the following parameters will be estimated:

Plasma:

AUC(0-∞)	Area under the concentration-time curve from time 0 (predose) extrapolated to infinite time
AUC(0-t)	Area under the concentration-time curve from time 0 (predose) to time of last quantifiable concentration
Cmax	Maximum observed concentration
λ_z	Terminal-phase rate constant
t _{1/2}	Terminal phase half life
Tmax	Time to first occurrence of Cmax
t _{lag}	Lag time
CL/F	Apparent oral clearance

V_z/F Apparent volume of distribution

Urine:

Ae total Total unchanged drug (total amount of drug excreted in urine), calculated by adding all the fractions of drug collected over all the allotted time intervals

Ae(t1-t2) Amount of drug excreted in urine in a time intervals for predose, 0 to 6, 6 to 12, 12 to 24, or 24 to 36, and 36 to 48 hours after dosing for participants with hepatic impairment; and predose, 0 to 2 hours, 2 to 4 hours, 4 to 6 hours, 6 to 8 hours, 8 to 12 hours, 12 to 24 hours, 24 to 36 hours, and 36 to 48 hours for participants with normal hepatic function

fe% Percentage of the given dose of drug excreted in urine, calculated as:

$$fe\% = (Ae \text{ total}/Dose) \times 100$$

CL_r Renal clearance of drug, calculated as: $Ae \text{ total}/AUC(0-t)$

AUC(0-12) Area under the concentration-time curve from time 0 (predose) to 12 hours

AUC(0-24) Area under the concentration-time curve from time 0 (predose) to 24 hours

AUC(0-48) Area under the concentration-time curve from time 0 (predose) to 48 hours

Plasma concentrations and urine concentrations of gepotidacin and the associated PK parameters will be listed, and summary statistics (n, mean, median, standard deviation [SD], minimum, maximum, and coefficient of variation [CV]) will be presented by day and treatment. Mean and individual plasma concentration versus time profiles will be presented graphically on linear and semilogarithmic scales.

The natural log-transformed plasma AUC(0-∞) and C_{max} values for gepotidacin in the hepatic impairment groups and normal hepatic function groups will be compared using an analysis of variance. Geometric mean ratios between hepatic impairment groups and normal hepatic function groups, and 90% CIs for the ratios of AUC(0-∞) and C_{max} for gepotidacin will be presented.

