2.2. Study Objective(s) and Endpoint(s)

Objectives	Endpoints
Primary Objectives	Primary Endpoints

 To compare the plasma PK parameters of a 1500 mg oral dose of gepotidacin in normal healthy participants to participants with mild, moderate, and severe hepatic impairment 	
 Plasma gepotidacin AUC(0-∞) and Cmax, as data permit.
Secondary Objectives	Secondary Endpoints

 To assess the safety and tolerability of gepotidacin administered as a 1500 mg oral dose in normal healthy participants compared with participants with mild, moderate, and severe hepatic impairment To compare the secondary plasma PK parameters of 1500 mg oral dose of gepotidacin in normal healthy participants with participants with mild, moderate, and severe hepatic impairment To compare the urine PK parameters of a 1500 mg oral dose of gepotidacin in normal healthy participants with participants with 	
 12-lead safety ECG readings, change from baseline in vital sign measurements (blood pressure and heart rate), monitoring of AEs, toxicity grading of clinical laboratory test results, and physical examinations Plasma gepotidacin AUC(0-t), Tmax, tlag, CL/F, Vz/F, λz, and t1/2, as data permit Urine gepotidacin PK endpoints: 
 Primary: Ae total, fe %, and CLr, as data permit Secondary: Ae(t1-t2), AUC(0-12), AUC(0-24), and AUC(0-48), as data permit

Objectives	Endpoints
mild, moderate, and severe hepatic impairment	
Exploratory Objectives	Exploratory Endpoints

• To evaluate the saliva PK parameters of a 1500 mg oral dose of gepotidacin in normal healthy participants compared with participants with mild, moderate, and severe hepatic impairment	
• Saliva gepotidacin PK endpoints:
○ Primary: AUC(0-∞) and Cmax, as data permit○ Secondary: AUC(0-t), Tmax, λz, t1/2, CL/F, Vz/F, and saliva to unbound plasma AUC(0-t) and AUC(0-∞) ratios (RAUC) of gepotidacin, as data permit.

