7.2.1.2. Derived Pharmacokinetic Parameters

Pharmacokinetic parameters will be calculated by standard non-compartmental analysis according to current working practices and using the currently supported version of WinNonlin. All calculations of non-compartmental parameters will be based on actual sampling times.

Plasma pharmacokinetic parameters listed below will be determined from the total plasma concentration-time data, as data permits.

Parameter	Parameter Description
AUC(0-t)	Area under the concentration-time curve from time 0 (predose) to time of last quantifiable concentration, to be calculated using the linear trapezoidal rule for each incremental trapezoid and the log trapezoidal rule for each decremental trapezoid
Tmax	Time to first occurrence of Cmax
tlag	Lag time before observation of drug concentrations in sampled matrix
t _{1/2}	Terminal half-life will be calculated as: $t_{1/2} = \ln 2 / \lambda_z$
λ_z	Terminal-phase rate constant
CL/F	The apparent oral clearance, calculated as: $CL/F = \text{Dose} / AUC(0-\infty)$
Vz/F	The apparent volume of distribution during the terminal phase, calculated as: $V_z/F = CL / \lambda_z$

NOTES:

- Additional parameters may be included as required.
- For the derivation of unbound plasma PK parameters; the total plasma PK parameters AUC(0-t) will be multiplied by 0.67, and the total plasma PK parameter CL/F will be divided by 0.67, to correct for the low plasma protein binding of gepotidacin (33%) observed in previous studies.

Pharmacokinetic parameters listed will be determined from the urine concentration-time data, as data permits.

Parameter	Parameter Description
Ae total	Total unchanged drug (total amount of drug excreted in urine), calculated by adding all the fractions of drug collected over all the allotted time intervals
Ae(t1-t2)	Amount of drug excreted in urine in time intervals for predose, 0 to 6, 6 to 12, 12 to 24, 24 to 36, and 36 to 48 hours after dosing for subjects with hepatic impairment; and predose, 0 to 2 hours, 2 to 4 hours, 4 to 6 hours, 6 to 8 hours, 8 to 12 hours, 12 to 24 hours, 24 to 36 hours, and 36 to 48 hours for subjects with normal hepatic function; calculated by multiplication of the urine concentration for a time interval and the length of this time interval.

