Study drug administration			X				
Blood collection for pharmacokinetics			X	X	X		See Section 10.1.2 for time points

Procedure ¹	Screening (up to 30 days prior to Day -1)	Check- in -1	Treatment Period (Days)			Follow-up (10 [±5] days postdose) or Early Termination	Notes
			1	2	3		
Urine collection for pharmacokinetics			X	X	X		Participants with normal hepatic function and participants with hepatic impairment will have different collection intervals See Section 10.1.2 for time points
Saliva collection for pharmacokinetics			X	X	X		See Section 10.1.2 for time points
AE/SAE review	X	X	←-----→			X	
Concomitant medication review		X	←-----→			X	

AE = adverse event, Clcr = estimated creatinine clearance; ECG = electrocardiogram, FDA = Food and Drug Administration; FSH = follicle-stimulating hormone; HIV = human immunodeficiency virus; PGx = pharmacogenetic, SAE = serious AE; WOCBP = women of childbearing potential.

¹ When coinciding with safety and/or pharmacokinetic assessments, electrocardiograms, vital signs, and pharmacokinetic blood collections should be performed in said order.

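### Ae(t1-t2) is summarised only by geometric statistics, which fail at zero, and over 0 to 12 h its intervals do not match between controls and impaired participants

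*SAP*

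**What the plan says.** **Endpoint.** SAP 2.2 lists, under the objective of comparing urine pharmacokinetics between normal and impaired participants, "Secondary: Ae(t1-t2), AUC(0-12), AUC(0-24), and AUC(0-48), as data permit".

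**Intervals.** SAP 7.2.1.2 defines Ae(t1-t2) for impaired participants as "Amount of drug excreted in urine in time intervals for predose, 0 to 6, 6 to 12, 12 to 24", then 24-36 and 36-48 h. Controls have predose, 0-2, 2-4, 4-6, 6-8, 8-12, 12-24, 24-36 and 36-48 h. The SAP's time and events table (10.1.1) says so openly: "Participants with normal hepatic function and participants with hepatic impairment will have different collection intervals". The value is "calculated by multiplication of the urine concentration for a time interval and the length of this time interval".

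**Summary statistics.** For parameter data, SAP 10.3.3 specifies "N, n, geometric mean, 95% CI of geometric mean, standard deviation (SD) of logged data and between geometric coefficient of variation". The parameters not ln-transformed are Tmax, tlag, CLr and the lambda_z descriptors; Ae(t1-t2) is not there. Protocol 10.3.1 planned arithmetic statistics for urine parameters: n, mean, SD, median, minimum, maximum and CV. SAP Table 1 (changes to the protocol-defined analysis) does not mention the switch.

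**NQ values.** Under concentration data, SAP 10.3.3 sets leading NQs to zero. Of trailing NQs it says "for individual plots and pharmacokinetic analyses these are dropped (set to missing) as they do not provide any useful information". The next line sets the same values to zero for summary statistics. The text speaks of drug in the blood, and no rule is specific to urine amounts.

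**The concern.** Ae(t1-t2) can legitimately be zero. A logarithmic summary cannot represent that, and tlag, another parameter that can be zero, is already exempt. The trailing-NQ rule then leaves open whether a collected late interval with no quantifiable drug counts as zero or drops out. A fully collected NQ interval is a known, small amount; treating it as missing discards the lowest values.

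The second issue does not depend on NQ values. The objective is a comparison, but over the first 12 h each group is tabulated on its own grid. At stake is whether a stated secondary endpoint can be read across groups in Table 3.5, which is both an interim and a final deliverable.

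**Working it through.** **1. The plan's own figures.** The documents give no figure for Ae(t1-t2). The only precision calculation (protocol 10.1, plasma) reproduces. With s = sqrt(ln(1+CV²)) and 8 per group, exp(t(0.95, 14 df) × s × sqrt(2/8)) − 1 gives 22.55%, 22.03% and 44.40% for CVs of 23.4%, 22.9% and 43.6%, against the stated 22.5%, 22.0% and 44.4%. It does not bear on this point, except that I borrow two of its CVs below.

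**2. Predose.** Gepotidacin within 12 months is an exclusion (protocol 6.2, criterion 11), and leading NQs are zero. All predose values are therefore zero, ln(0) does not exist, and neither do the geometric mean, its CI, the SD of logs or CVb. Arithmetic statistics give mean 0 and SD 0.

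**3. Late intervals, if some values are NQ.** Assumptions, none from the documents for urine: Ae is lognormal; the lowest share p of one group is NQ; CV is 22.9% to 80%; p is 12.5% to 50%.

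*NQ set to zero.* The geometric mean is undefined once one of 8 values is NQ. That probability is 1 − (1−p)^8, which is 66%, 90% and 99.6% for p = 12.5%, 25% and 50%.

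*NQ set to missing.* The geometric mean is multiplied by exp(s × φ(z_p)/(1−p)). For CV 43.6%, s = 0.417; at p = 25%, φ = 0.318 and exp(0.417 × 0.318/0.75) = 1.19. If the other group's true geometric mean is 1.5 times higher and the same limit applies to it, its own factor uses z_p − ln(1.5)/s, and the apparent ratio follows:

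| CV | NQ share | Factor on geometric mean | True ratio 1.5 appears as |
|---|---|---|---|
| 22.9% | 12.5% / 25% / 50% | 1.05 / 1.10 / 1.20 | 1.42 / 1.37 / 1.28 |
| 43.6% | 12.5% / 25% / 50% | 1.10 / 1.19 / 1.39 | 1.38 / 1.32 / 1.22 |
| 80% | 12.5% / 25% / 50% | 1.18 / 1.35 / 1.75 | 1.36 / 1.29 / 1.19 |

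With no NQ values the factor is 1.00.

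**4. Intervals side by side.**

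| Window | Impaired rows | Control rows |
|---|---|---|
| 0-6 h | 0-6 | 0-2, 2-4, 4-6 |
| 6-12 h | 6-12 | 6-8, 8-12 |
| 12-48 h | 12-24, 24-36, 36-48 | same |

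Three of the five impaired post-dose rows have a counterpart. The control rows nest exactly, but a reader cannot rebuild the missing rows from the table. The geometric mean of a sum is at least the sum of the geometric means, with equality only when participants' values are proportional across intervals. Under mono-exponential excretion with an assumed half-life of 6, 12 or 18 h, the unmatched 0-12 h window holds (1 − 2^(−12/h))/(1 − 2^(−48/h)) = 75%, 53% or 44% of 48-h excretion.

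**5. What is not touched.** Ae total is a sum over intervals, and fe% and the numerator of CLr follow from it. If the sum is taken over available intervals, a dropped trailing NQ adds nothing, just as zero would. The formal urine comparisons are AUC(0-48) and CLr only (SAP 7.2.4.1, Table 3.8).

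**The case against.** A reader might infer that late excretion in controls will be inflated and that slower excretion in hepatic impairment will be understated. The documents do not support that. It requires the missing-value branch to govern Ae, late urine to fall below the quantification limit, and more of this in controls. Missing is the natural reading for a derived parameter, but the zero line stands directly beneath it, and neither is tied to urine amounts. Nothing says which group would have more NQ values.

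There may be none. About 20% of an oral dose appears as parent drug in urine (protocol 3.1), or 300 mg of 1500 mg. At half-lives of 6 to 18 h, 36-48 h holds 1.2% to 11% of 48-h excretion, roughly 3.5 to 33 mg. In an assumed 0.5 to 1.5 L of urine that is about 2 to 66 µg/mL, so a typical participant would be NQ only with a limit above about 2 µg/mL. Losses would also show, since N and n are both reported.

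On the intervals, the different schedules are a disclosed protocol choice. Urine AUC(0-12) is derived over the same window in both groups, although it measures concentration over time and not amount. Listing 45 gives individual values, and the SAP allows additional parameters. So no data are lost, and it would be too strong to say that no early comparison is possible. What stands is that the planned table contains no comparable Ae(t1-t2) row there.

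The predose cell carries no treatment information, and I accept that an empty cell changes no conclusion.

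**Conclusion.** The point holds as a minor one. Certain from the text: Ae(t1-t2) defaults to geometric summaries; these do not exist predose; the SAP does not say which NQ branch governs Ae; and no Ae(t1-t2) row over 0-12 h is comparable between groups. Conditional: if a late interval is NQ in any participant, its geometric mean is undefined or biased upward. The factors of 1.05 to 1.75 rest wholly on assumed CVs and NQ shares and are not predictions for this trial.

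Nor should a reader infer that the main conclusions are at risk. Ae(t1-t2) is descriptive, Ae total and fe% are not materially affected under the summing rule above, and the plasma primary endpoints and the plasma thresholds for entering Part 2 are untouched. The same gap could leave urine AUC(0-48) without its last point, but nothing in the documents allows that effect to be sized, and I draw no conclusion from it.

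**What to change.** 1. For Table 3.5, derive per control participant Ae(0-6) = Ae(0-2) + Ae(2-4) + Ae(4-6) and Ae(6-12) = Ae(6-8) + Ae(8-12). Present both groups on 0-6, 6-12, 12-24, 24-36 and 36-48 h. The sums are like for like only if Ae is an amount; SAP 7.2.1.2 words it as concentration times interval length, so the amount formula needs confirming at the same time.
2. In SAP 10.3.3, add Ae(t1-t2) to the parameters not ln-transformed and use the protocol 10.3.1 statistics.
3. State that a fully collected NQ urine interval counts as zero amount, and report the number of NQ participants per interval.

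**Cost.** SAP wording and a few lines of programming; no new samples or data. Ae(t1-t2) would sit on a different summary scale from Ae total and fe%.

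Setting NQ to zero also understates late excretion. The arithmetic mean becomes exp(s²/2) × Φ(s − z_p), taking the true geometric mean as 1. At CV 43.6% that is 0.94 at 25% NQ and 0.72 at 50%, against a true 1.09. A true ratio of 1.5 would then appear as 1.5 × Φ(s + ln(1.5)/s − z_p)/Φ(s − z_p) = 1.71 or 2.08. The error is small only when few values are NQ. This is why the median and the NQ counts belong in the table: with 8 participants the median is unaffected by up to three NQ values.
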